3.2 Test design and study method selection

3.2.1 Sample collection

Tissue sections fixed in neutral formaldehyde and embedded in paraffin were detected.

3.2.2 Sample data

- (1) Sample information
 - A) Patient visiting No. / medical record No. / specimen No., age, sex, and pathological diagnosis result
 - B) HE staining results of samples, indicating tumor area.
- (2) Pathological examination confirmed glioma, other brain tumors or normal tissues.
- (3) Number of samples: each sample contains 10 slices with a thickness of 10 μ m, and the tumor content is not less than 50%.

3.2.3 Sample storage

FFPE samples should be stored at room temperature.

3.2.4 Kit source:

- (1) The kits were provided by Genetron Health (Beijing) Co., Ltd.
- (2) Test instrument: BIO-RAD: CFX96 Real-Time PCR Detection System or LIFE: 7500 Fast Dx Real Time PCR Instrument.

[figure not shown]
3.2.5 Reference method

Sanger sequencing was used as the control method. Sequencing fragments cover the target nucleic acid segments, sites and corresponding types amplified by the assessment reagent. After the sequencing reaction is over, submit a representative sample sequencing map and result analysis data.

3.2.6 Testing process

The test samples were tested in strict accordance with the kit operation instructions.

3.3 Study technology route

3.4 Quality control method

- (1) The clinical verification institutions are all three-level medical institutions above the provincial level with the ability to conduct the clinical research technology and equipment to ensure the quality of clinical diagnosis.
- (2) Each clinical trial institution has 1 project director, and 1 to 3 fixed project members. Strictly follow the requirements of the clinical trial protocol. The reporting institution appoints 1 inspector to monitor and cooperate with the team leader institution and the trail institution at any time. The technical personnel of the team leader institution keep close contact with each trail center at any time.
- (3) The test kit detection and reference method detection are carried out in accordance with the blind method.
- (4) Hospital laboratories participating in clinical trials should establish standard operating procedures and quality control procedures for experimental observation indicators. The test report must be complete, which must include date, test items, test results and their normal range. The person concerned should sign. Each test is set up control, and strictly in accordance with the requirements of the manual.
- (5) Training: Before the start of the experiment, conduct protocol training for all personnel participating in the experiment, and conduct training and assessment for clinical research staff, so that clinical trial personnel able to quickly become familiar with and master the fluorescence PCR technology and the applicable instruments, operating methods, and technical performance etc. of the kit.
- (6) This protocol has been determined through repeated communication and research between the experimental institution and the clinical institution, and must be strictly implemented. Any changes in the plan must be approved by the team leader (master) institution.

4 Evaluation method

4.1 Evaluation method for reagents to be tested

- 1) The Ct value of FAM channel of positive control substance was ≤ 18 , and the amplification curve had obvious exponential growth period.

- (2) The blank control FAM channel had no amplification curve, or the amplification curve was slightly oblique without significant exponential growth, and the Ct value of FAM channel was ≥ 24 .
- (3) Result determination: After determining Ct value and ΔCt value according to the above steps, determine the result according to the following table.

Table 2 Result determination

Mutation type	Negative	Negative		Positive	
IDH1 R132H	There was no obvious amplification of FAM channels Or the Ct value is not displayed	Ct value < 25	$\Delta Ct > 8$	Ct value < 25	$\Delta Ct \leq 8$

4.2 Evaluation method for nucleic acid sequence determination

- (1) The results of the positive reference substance tested on the machine for nucleic acid sequence determination were positive, and the results of the blank reference substance should be in line with expectations without mutation detection.
- (2) Determination of reagent results: the sequencing software Mutation Surveyor was used to interpret the results. When 6695 G>GA, corresponding mutation is indicated; otherwise, no mutation is indicated.

4.3 Evaluate the conformity between the kit and the reference method

- (1) If the results to be tested and the reference results are both positive or negative, it is regarded as in conformity.
- (2) In the event that the result to be tested is positive and the reference result is negative, or the result to be tested is negative and the reference result is positive, it is recorded as non-conformity.
- (3) If the result to be tested fails and the reference method has confirmed results, it shall be recorded as non-conformity. The reasons and results of the non-conformity shall be truthfully recorded, and the comparison results shall be repeatedly confirmed when necessary.
- (4) Complete subsequent statistical analysis based on the above statistical results.

5 Statistical methods

Statistical analysis of clinical study data: Kappa test was used for statistical analysis of the comparison between the kit test results and gene sequencing test results, and then the difference between the results obtained by the two methods was compared. If $\text{Kappa} > 0.6$, it was proved that there was no statistical difference between the two methods in detecting IDH1 gene mutations in glioma samples.

6 Duration of clinical trials and its reasons

The clinical study lasted about 6-8 months from the drafting of the protocol, project approval, ethical review, agreement signing, specimen collection, the beginning of the test to the end of the trial, and the report and seal are completed. If the sample collection is smooth and the number of samples meets the test requirements, the clinical trial time can be shortened; if it is not smooth, the time can be appropriately extended.

7 Inclusion criteria, exclusion criteria and rejection Criteria

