7.3 Rejection Criteria

- (1) Samples considered by the researcher to be unsuitable for continuing clinical trials, such as samples that have not been prepared in accordance with the required steps.
- (2) Samples with unqualified genomic DNA quality, such as:
 - ① DNA concentration is less than 10ng/μL;
 - ② Genomic DNA was severely degraded or had insufficient purity, and OD260/OD280 exceeded the range of 1.6~2.0.
- (3) Samples whose repeated test results of reference methods failed.
- (4) Samples with incomplete clinical basic information (patients' visiting No. / medical record No./specimen No., age, sex, pathological diagnosis result).

8 Provisions for amendments to clinical trial protocols

Any modification to the protocol during the test should be explained, and the time, reason, process and record of the modification should be elaborated in detail, and its impact on the evaluation of the whole study results should be demonstrated.

9 Ethical issues and explanations of clinical trials

This clinical trial verification test uses the patient's pathological specimens in the previous treatment process. It is limited to in vitro diagnosis, does not directly contact the patient, does not cause any harm to the patient, and only compares the performance of the reagent with the control reagent. The results are only used for study and analysis related to this test, and will not guide the diagnosis and treatment of patients based on this, so it will not have any adverse effects on the human body.

This clinical trial strictly complies with the "Declaration of Helsinki", and this clinical verification trial involves relevant patient data. Such as: Patient visiting No. / medical record No. / specimen No., age, sex, pathological diagnosis result, etc. The hospital and Genetron Health (Beijing) Co., Ltd. will jointly undertake the confidentiality of the patient information, and the clinical trial operator and clinical validation unit promise not to disclose the content related to the subject specimen.

Therefore, the clinical trial was verified to submit an informed consent exemption to the ETHICS Committee.

10 Data processing and record keeping

It is required to keep all experimental records during the clinical trial, the results should be objective, timely and serious, and the operator and operation time should be recorded. Medical institutions shall keep the clinical trial data for five years after the termination of the trial.

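### Section 4.3(3) allows discretionary repeats of non-conforming results only (narrowly read, kit failures only), and nothing ties kappa to first results, so the Kappa > 0.6 criterion is open to one-sided bias

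*Combined protocol and SAP*

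**What the plan says.** Section 4.3 of the combined protocol and SAP sorts each sample into conformity or non-conformity.

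- Item (1): "If the results to be tested and the reference results are both positive or negative, it is regarded as in conformity". No repeat is attached.
- Item (2): positive against negative, in either direction, is non-conformity. No repeat is mentioned in this item.
- Item (3): "If the result to be tested fails and the reference method has confirmed results, it shall be recorded as non-conformity". It continues: "The reasons and results of the non-conformity shall be truthfully recorded, and the comparison results shall be repeatedly confirmed when necessary".
- Item (4): "Complete subsequent statistical analysis based on the above statistical results".

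Section 5 then states that "Kappa test was used for statistical analysis of the comparison between the kit test results and gene sequencing test results", with one success rule: "If $\text{Kappa} > 0.6$, it was proved that there was no statistical difference between the two methods".

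Three other places bear on repeats. Section 3.2.6 refers to the kit instructions ("The test samples were tested in strict accordance with the kit operation instructions"), which are not part of the document. Section 3.4(3) requires blinded testing by both methods but does not mention repeats. Section 7.3(3) rejects samples whose repeated reference tests failed, so some retesting by sequencing is already expected.

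**The concern.** The repeat depends on the comparison that the trial is meant to measure. A pair that disagrees may be run again, while the plan provides no second run for a pair that agrees by chance or through a shared error. The plan does not say who decides that a repeat is necessary, which assay is repeated, how many times, whether the repeat is blinded, or which result then enters kappa.

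If the repeated result enters, agreement is corrected in one direction only. Kappa > 0.6 is the only stated success criterion, so a borderline kit could pass because of the retest practice. A good kit would pass anyway, but its reported kappa could be too high.

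**Working it through.** **Inputs.** From the documents: at least 1,000 samples (Section 3.1) and Kappa > 0.6 (Section 5). The documents give no agreement, repeat-flip or failure rates and no expected mutation prevalence, so these are assumptions: n = 1,000, and 40% prevalence unless stated. There is no derived figure in the plan to reproduce.

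**Formula.** Let a, b, c, d be kit+/seq+, kit+/seq−, kit−/seq+, kit−/seq−. Then kappa = 2(ad − bc)/D, with D = (a+b)(b+d) + (a+c)(c+d).

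**Step 1: direction for valid discordant pairs.** Moving one pair from b to a (sequencing call changes) raises ad − bc by c + d and changes D by (c+d) − (a+b). Kappa falls only if (ad − bc)[(c+d) − (a+b)] > (c+d)D. When kappa is between 0 and 1, ad − bc is at most D/2, so the left side is at most (c+d)D/2 and a fall is impossible. The other moves follow by symmetry. Exact enumeration of all tables with 2 to 25 samples gave 40,900 defined moves out of cell b: 40,300 raised kappa, 600 left it unchanged (all at kappa = 0) and none lowered it. A repeat that confirms the discordance changes nothing.

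**Step 2: size for valid discordant pairs.** Kit repeats flip to agree with sequencing (cells a/b/c/d):

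| Positive/negative agreement | First results | 10% of discordant pairs flip | 25% flip |
|---|---|---|---|
| 80/80% | 320/120/80/480: 0.590 | 328/108/72/492: 0.631 | 340/90/60/510: 0.691 |
| 90/90% | 360/60/40/540: 0.793 | 364/54/36/546: 0.814 | 370/45/30/555: 0.845 |
| 95/98% | 380/12/20/588: 0.933 | 382/10.8/18/589.2: 0.940 | 385/9/15/591: 0.950 |

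First cell in full: 2(320×480 − 120×80)/(440×600 + 400×560) = 288,000/488,000 = 0.590. If the sequencing call flips instead at 80/80%, the results are 0.632 and 0.693.

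**Step 3: where the verdict changes.** With equal positive and negative agreement, kappa = 0.6 needs 80.5% on first results, 78.3% with 10% flips and 74.0% with 25% flips. Replacement therefore decides the outcome only at 78.3–80.5% or 74.0–80.5% agreement. At 20% prevalence the bands are 83.4–85.0% and 80.1–85.0%.

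**Step 4: kit failures.** Suppose 5% of kit runs fail and repeats agree as often as first results. Failures counted in the cell opposite to sequencing, against all failures replaced by repeats:

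| Agreement | Counted as disagreement | Replaced | Verdict changes? |
|---|---|---|---|
| 80/80% | 304/144/96/456: 0.510 | 0.590 | no, fails both ways |
| 80/85% | 304/115.5/96/484.5: 0.563 | 320/90/80/510: 0.647 | yes |
| 90/90% | 342/87/58/513: 0.702 | 0.793 | no, passes both ways |
| 95/98% | 361/41.4/39/558.6: 0.833 | 0.933 | no, passes both ways |

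At 2% failures and 80/85%, the values are 0.613 and 0.647, both passing. Treating failure as a third category instead of the opposite cell gives 0.584 rather than 0.563 (5%) and 0.621 rather than 0.613 (2%).

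The direction is not fixed for failures. Take 400/100/100/400 (kappa 0.600) with 20 failures left out. If all 20 repeat as discordant, the table is 400/110/110/400 and kappa is 0.569. With failure as a third category, the change is from 0.577 to 0.569.

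**The case against.** The strongest reply is that the plan never says a repeat replaces anything. Items (2) and (3) record the sample as non-conforming, item (3) asks for truthful recording, and item (4) analyses the results above it. The most direct reading may be that the recorded classifications are analysed and the repeat is for the record. A reader might infer that the plan instructs replacement. It does not; it only leaves replacement open. That part of the reply stands, but no sentence settles the matter, and the point concerns what the text permits.

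Second, the repeat sentence sits in item (3), whose subject is a failed kit run. It may not reach the positive/negative discordance of item (2). This also stands: the 80/80% figures in Step 2 apply only on the broad reading.

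Third, a reader might infer that repeats can only raise kappa. That holds for a valid discordant pair when one method's call is replaced, apart from no change at kappa = 0. It does not hold for failures left out of the table or made a third category (Step 4). If both methods flip, the pair stays discordant and the change is negligible (0.60064 to 0.60058 for 400/120/80/400).

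Fourth, the effect on the verdict is confined to a narrow band of agreement, and nothing in the documents places the kit there. This is right and limits the weight of the point.

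**Conclusion.** The concern holds in limited form. The plan allows a repeat triggered by the outcome, at someone's discretion, for non-conforming results or for kit failures only, and does not fix which result enters its sole success criterion. Where a repeat replaces one method's call in a valid discordant pair, the bias has one direction.

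On the assumed inputs the verdict turns only for a kit with modest agreement. At 95/98% kappa could be overstated by 0.007 (10% flips) to 0.017 (25% flips) without affecting the pass. For failures at 5%, the verdict changes at 80/85% agreement but not at 80/80%, 90/90% or 95/98%.

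The documents do not support the stronger conclusions that replacement will occur or that a pass by this kit would be unsafe. Confidence is medium, because both the scope of the clause and the rates are unknown. The plan should be changed, since the rule has to be fixed before results are seen and costs almost nothing.

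**What to change.** In 4.3(4) and Section 5, state that:

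1. The primary kappa uses the first valid blinded result of each method.
2. Retests are allowed only for invalid or failed runs: for the kit under the instructions invoked in 3.2.6, for sequencing as 7.3(3) implies. They are decided without knowledge of the other method's result.
3. Repeats of non-conforming pairs are listed separately and do not replace first results.
4. Kit failures that remain after permitted retests count as disagreement, in line with how 4.3(3) already records them, for example in the cell opposite to the sequencing result.

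In 4.3(3), state whether the repeat clause covers all non-conformity or kit failures only.

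The cost is a few sentences. No extra testing is needed, because Section 10 already provides the records: "It is required to keep all experimental records during the clinical trial". The downside is that the reported kappa may be slightly lower.

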By using this product to detect the IDH1 R132H gene mutation in the cancer cells of patients with glioma, compare it with the results of nucleic acid sequence determination, and combine the results of clinicopathological typing to confirm and evaluate the safety and effectiveness of this product.

3 Trial Design

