7.1 Inclusion criteria

- (1) Be able to provide samples timely according to the requirements of the protocol.
- (2) The pathological examination conforms to the type of tissue sample listed in Table 1, and the tumor content is not less than 50%.
- (3) The sample should have corresponding basic clinical information, including: the patient's visiting No. / medical record No./specimen No., age, sex, and pathological diagnosis result.

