7.2 Exclusion criteria

Those who do not meet any of the above conditions are excluded.

Rationale: Included glioma, other brain tumors, and normal samples should be statistically significant and the conclusions obtained are scientifically valid. The selection of subjects for this study, while excluding research-related influencing factors, has no adverse effect on the health of the subjects.

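### The kappa > 0.6 criterion is not limited to glioma samples, although the conclusion is about glioma; pooled non-glioma negatives would inflate it

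*Combined protocol and SAP*

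**What the plan says.** **Criterion.** Section 5 states that a "Kappa test was used for statistical analysis of the comparison between the kit test results and gene sequencing test results". If kappa exceeds 0.6, the plan takes it as proved that "there was no statistical difference between the two methods in detecting IDH1 gene mutations in glioma samples". This is the only numeric criterion for agreement, and no analysis set is named.

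**Purpose.** Section 2 is about using the product to "detect the IDH1 R132H gene mutation in the cancer cells of patients with glioma".

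**Samples.** Section 3.2.2 lists "Pathological examination confirmed glioma, other brain tumors or normal tissues". The rationale in Section 7.2 repeats this: "Included glioma, other brain tumors, and normal samples should be statistically significant and the conclusions obtained are scientifically valid". Section 3.1 asks for at least 1,000 samples in total and does not divide them between glioma and other tissue.

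**Entry and removal.** Section 7.1 requires that "The pathological examination conforms to the type of tissue sample listed in Table 1, and the tumor content is not less than 50" per cent, and Section 7.2 adds "Those who do not meet any of the above conditions are excluded". The rejection criteria in Section 7.3 concern preparation, DNA quality, failed reference tests and missing data. Being non-glioma is not among them.

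**Subtype output.** The only planned result by subtype is R132H incidence (Section 3.1). No agreement measure by tissue type is planned.

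**The concern.** The data behind the criterion and the population in the conclusion are not stated to be the same. Someone following Section 5 literally could pool every tested sample. Normal tissue and other brain tumours would be expected to be mostly negative by both methods, although the documents give no mutation rate for them. Samples that are easy to agree on would then lift a statistic that is used to make a claim about glioma.

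Two analysts could follow this plan and report different kappas from the same data. The overstatement would depend on how many non-glioma samples the sites happened to supply, and no planned output would show it. For a kit somewhat below the threshold in glioma, the pass/fail result itself could change.

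**Working it through.** **Inputs.** From the documents: the 0.6 threshold (Section 5) and the minimum of 1,000 samples (Section 3.1). The 1,000 cannot be reproduced, because no expected kappa, precision or power is given for it. Assumed: glioma prevalence, agreement rates, non-glioma share and non-glioma error rate.

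**Direction.** Let *a* = both positive, *b* = kit-only positive, *c* = reference-only positive, *d* = both negative.

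κ = 2(ad − bc) / [(a+b)(b+d) + (a+c)(c+d)]

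Differentiating in *d* with the other cells fixed, the numerator of the derivative is

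2a[b(a+b) + c(a+c)] + 2bc(2a+b+c),

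which is positive when a > 0 and there is any discordance. Each added concordant negative therefore raises kappa.

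**Base case.** 45% prevalence, 75% positive and 80% negative agreement, non-glioma samples all concordant negative. With 800 gliomas: a = 270, b = 88, c = 90, d = 352.

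- Glioma only: po = 622/800 = 0.7775; pe = 0.4475×0.45 + 0.5525×0.55 = 0.50525; κ = (0.7775 − 0.50525)/(1 − 0.50525) = 0.550.
- Add 200 concordant negatives: po = 822/1,000 = 0.822; pe = 0.358×0.36 + 0.642×0.64 = 0.53976; κ = 0.613.

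| Non-glioma share | po | pe | κ | κ > 0.6? |
|---|---|---|---|---|
| 0% | 0.7775 | 0.50525 | 0.550 | no |
| 10% | 0.79975 | 0.51848 | 0.584 | no |
| 20% | 0.822 | 0.53976 | 0.613 | yes |
| 30% | 0.84425 | 0.5691 | 0.639 | yes |

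Solving pooled κ = 0.6 for the share gives 15.3%.

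**Prevalence** (same agreement rates, 20% share). Pooled κ is 0.489 at 20%, 0.561 at 30%, 0.601 at 40%, 0.622 at 50% and 0.630 at 60%. The break-even prevalence is 39.7%, or 34.0% at a 30% share. For orientation, take the background section's IDH1/2 frequencies and multiply by 0.9 × 0.9 (IDH1 share of mutations, R132H share of IDH1). This gives about 56–65% in grade II–III types (0.692×0.81 = 0.561; 0.798×0.81 = 0.646), 59% in secondary glioblastoma and about 4% or less in primary glioblastoma. Overall prevalence therefore depends on the case mix.

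**Non-glioma false positives** (45% prevalence). Pooled κ falls back below 0.6 when the kit-only positive rate in non-glioma exceeds 3.4% at a 20% share, or 6.5% at a 30% share.

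**Width of the reversal window.** With equal positive and negative agreement *q* and a 20% share, solve glioma κ = 0.6 and pooled κ = 0.6 for *q*:

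| Prevalence | q where the verdict differs | Glioma κ in that range |
|---|---|---|
| 30% | 80.1–82.1% | 0.56–0.60 |
| 45% | 76.7–80.1% | 0.53–0.60 |
| 60% | 75.1–80.5% | 0.49–0.60 |

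**Outside the window** (45% prevalence, 30% share). At 90%/90% agreement, κ is 0.798 in glioma and 0.839 pooled. At 95%/95% it is 0.899 and 0.919. The decision does not change.

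**The case against.** - **The plan never says that it pools.** Section 5's conclusion names glioma samples and Section 2 limits the purpose to glioma, so a glioma-only kappa is a fair reading. It remains unstated, however: the phrase describes the conclusion, not the data analysed.
- **The entry rules may keep non-glioma samples out.** The rows of Table 1 available for this review (Classes II–IV) are all glioma types, and normal tissue cannot meet the tumour-content rule. If Sections 7.1 and 7.2 govern, normal tissue contributes nothing. Yet Sections 3.2.2 and 7.2 name it as included, so this is a contradiction rather than a safeguard. Whether other brain tumours are also barred cannot be settled, because the opening of Table 1 was not in the text reviewed.
- **The illustration uses a kit just below the threshold.** This is correct. The reversal window is about 2 to 5 percentage points of agreement wide, and the agreement rates have no source in the documents.
- **Non-glioma samples may not all be concordant.** Section 4.3 counts a kit failure with a confirmed reference result as a non-conformity. If such failures are tabulated as discordant, they count towards the 3.4% and 6.5% limits. That narrows the inflation, but it is another reason not to mix the populations.
- **Nothing is lost.** Diagnosis and non-conformities are recorded, so a glioma kappa could be derived later. None is planned as the basis for the decision.

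**Conclusion.** The concern holds. Section 5 leaves the population of its only numeric criterion undefined, and other sections describe non-glioma samples as included. The direction of the effect is certain for concordant negatives. Its size is conditional on pooling, on the non-glioma share, on near-complete concordance there and on glioma prevalence, none of which the documents fix.

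Under the base-case assumptions a failing glioma kappa of 0.550 becomes a passing 0.613 at a 20% share. The decision changes only for a kit somewhat below 0.6 in glioma. For a kit with about 90% agreement and 30–60% prevalence, the consequence is an overstated kappa and not a wrong verdict.

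The conflict over normal tissue between Section 3.2.2 and the Section 7.2 rationale on one side, and the tumour-content and exclusion rules on the other, stands whatever the kappa arithmetic shows.

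**What to change.** - In Section 5, state that the kappa compared with 0.6 is calculated in pathology-confirmed glioma samples only.
- Report other brain tumours and normal tissue separately, as negative percent agreement with sequencing. Keep any pooled kappa descriptive.
- Reconcile Sections 3.2.2, 7.1 and 7.2 on which samples enter, and say how the tumour-content rule applies to normal tissue.

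The cost is wording plus a subset flag taken from the pathological diagnosis, which is already mandatory for every sample. The downside is a smaller set for the decision and possibly a lower kappa.

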	Class II	Diffuse astrocytoma, mixed oligoastrocytomas, oligodendrogloma, pleomorphic xanthoastrocytoma, hairy myxoid astrocytoma
	Class III	Anaplastic astrocytoma, anaplastic oligodendrogloma, anaplastic oligoastrocytomas
	Class IV	Primary and secondary glioblastoma

Isocitrate dehydrogenase (IDH), located in the long arm of chromosome 2 (2q33), is a key rate-limiting enzyme in the tricarboxylic acid cycle, providing energy for cell metabolism and precursors of biosynthesis. There are three isomerases in the IDH gene family (IDH1, IDH2 and IDH3). IDH1 or IDH2 mutations lead to the accumulation of 2-hydroxyglutaric acid, another new metabolite, in cells, which can not only lead to abnormal histone modification, but also increase the activity of VEGF pathway, thereby inducing tumorigenesis. The data showed that IDH1/2 gene mutation was an early genetic mutation in the development of glioma. It usually occurs in young adults and

adolescents with diffuse glioma. IDH1/2 mutation had a certain distribution pattern corresponding to WHO classification, which was mainly distributed in grade II~III oligodendrogloma (69.2%), astrocytoma (79.8%), oligoastrocytomas (75.5%) and grade IV secondary glioblastoma (73%), but rare in primary glioblastoma (<5%) and childhood glioblastoma.

IDH1 mutations accounted for more than 90% of IDH1 and IDH2 gene mutations, among which IDH1 R132H (CGT>CAT, arginine replaced by histidine) mutations were the most common, accounting for about 90% of IDH1 mutations.

The National Comprehensive Cancer Network (NCCN) Clinical Practice Guidelines for Central Nervous System Cancer (V1, 2015) include the presence or absence of IDH1 or IDH2 gene mutations as one of the indicators to assess the risk type of patients with low-class glioma. The Chinese Guidelines for molecular Diagnosis and Treatment of glioma (2014) also included IDH1 or IDH2 gene mutation as the preferred molecular marker for molecular pathological typing (grade I evidence).

At present, the gold standard method for clinical detection of IDH gene mutation is nucleic acid sequencing. However, this method is time-consuming and laborious to determine the detection results, and the operation process is complex, so it is difficult to widely apply this technique in clinical practice.

2 Research Purpose

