3.1 Overall Design of the Trial

This study followed the principle of synchronous blind method. Enrolled cases were coded and compared with the nucleic acid sequence determination of the control method (gold standard). Results were determined independently according to the critical value or interpretation requirements provided by each method, and relevant statistics were conducted. Combined with the results of clinicopathological classification, the incidence of IDH1 gene R132H mutation in different subtypes was counted to evaluate the clinical application performance of this product

The total number of samples for clinical research should be no less than 1,000 cases, and clinical trials should be carried out in no less than 3 (including 3) provincial health care institutions or specialized hospitals to ensure that the results are statistically significant. All samples should have corresponding basic clinical information, including: patient visiting No. / medical record number/specimen number, age, sex, pathological diagnosis result, etc.

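### Section 5 judges the kit by one unstratified kappa above 0.6, which partly reflects the unfixed mix of glioma types and can pass a kit that misses 38% of mutations

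*Combined protocol and SAP*

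**What the plan says.** Section 5 gives the whole agreement analysis: "Kappa test was used for statistical analysis of the comparison between the kit test results and gene sequencing test results". The same sentence adds that the difference between the two sets of results is then compared, but it names no test. The only numerical rule follows. If kappa exceeds 0.6, "it was proved that there was no statistical difference between the two methods in detecting IDH1 gene mutations in glioma samples". No confidence interval, strata, or positive or negative percent agreement is specified.

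Sections 3.2.2 and 7.1 require a pathological diagnosis for every sample. Its one stated analytic use is in Section 3.1, where "the incidence of IDH1 gene R132H mutation in different subtypes was counted". Section 3.1 also sets a total of at least 1,000 samples, with no quota by diagnosis.

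The background, before Section 2, gives IDH1/2 mutation frequencies of 69.2% in oligodendroglioma, 79.8% in astrocytoma, 75.5% in oligoastrocytoma and 73% in secondary glioblastoma, "but rare in primary glioblastoma (<5%) and childhood glioblastoma". It adds that "IDH1 mutations accounted for more than 90% of IDH1 and IDH2 gene mutations", and that within IDH1 the R132H "mutations were the most common, accounting for about 90% of IDH1 mutations".

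**The concern.** Kappa removes chance agreement using only the overall proportions positive on each method. When types with very different mutation frequencies are pooled, part of the contrast between types counts as agreement between methods. Restricting the analysis to glioma does not remove this, because the spread lies within glioma.

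Kappa above 0.6 is the only numerical success rule. If its value moves with the mix of diagnoses, and the plan does not fix that mix, the same kit can pass or fail according to which blocks the sites supply. At stake is a conclusion of no difference from sequencing for a kit that misses a large share of mutations. Counting R132H incidence by subtype would not reveal this reliably, because incidence is not agreement.

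**Working it through.** **The plan's own figure.** The 1,000-sample minimum comes with no alpha, power, expected kappa or case mix, so it cannot be reproduced. It is not used below except as context.

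**Step 1: R132H frequency by type.** The documents do not state these. They are derived as IDH1/2 frequency x 0.90 x 0.90 = IDH1/2 frequency x 0.81, assuming that the two shares hold in every type.

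| Type | IDH1/2 | R132H |
|---|---|---|
| Oligodendroglioma | 69.2% | 56.1% |
| Secondary glioblastoma | 73% | 59.1% |
| Oligoastrocytoma | 75.5% | 61.2% |
| Astrocytoma | 79.8% | 64.6% |
| Primary glioblastoma | <5% | at most 4.05% |

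The first four, in equal parts, average 60.2%. They are called mutation-rich below, and w is their share of all gliomas. The plan does not give w, so it is varied.

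**Step 2: formula.** Kappa = (po - pe)/(1 - pe). With R132H frequency f, positive agreement S and negative agreement T:
- po = fS + (1 - f)T
- kit-positive proportion k = fS + (1 - f)(1 - T)
- pe = fk + (1 - f)(1 - k)

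**Step 3: a kit with S = 0.62 and T = 0.98 in every type.**
- Astrocytoma: po = 0.7473, pe = 0.4730, kappa = 0.2743/0.5270 = 0.52.
- Primary glioblastoma: po = 0.9654, pe = 0.9188, kappa = 0.0466/0.0812 = 0.57.
- Oligodendroglioma 0.57, oligoastrocytoma 0.54, secondary glioblastoma 0.55.

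Every type is below 0.6. Pooled at w = 0.3:
- f = 0.3 x 0.6024 + 0.7 x 0.0405 = 0.2091
- po = 0.9047 and k = 0.1454
- pe = 0.1454 x 0.2091 + 0.8546 x 0.7909 = 0.7063
- kappa = 0.1984/0.2937 = 0.676

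| w | 10% | 20% | 30% | 40% | 50% | 60% | 80% |
|---|---|---|---|---|---|---|---|
| Pooled kappa | 0.657 | 0.674 | 0.676 | 0.669 | 0.659 | 0.644 | 0.604 |

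The kit passes throughout this range and misses 1 - 0.62 = 38% of the mutations that sequencing finds.

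**Step 4: the mix can decide the result.** A kit with S = 0.70 and T = 0.90 has kappa 0.56 at a frequency of 61% and 0.30 at 4%. Pooled, it has 0.58 at w = 30% (fail) and 0.61 at w = 50% (pass). The kit is the same; only the mix differs.

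**Step 5: benchmark for the criterion.** Suppose that every mutation-rich sample is called positive and every primary glioblastoma negative, with no DNA tested. At w = 0.3, po = 0.8524 and pe = 0.6164, so kappa = 0.2360/0.3836 = 0.615.

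| w | 10% | 20% | 30% | 40% | 50% | 80% |
|---|---|---|---|---|---|---|
| Pooled kappa | 0.570 | 0.616 | 0.615 | 0.595 | 0.562 | 0.355 |

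Within each type this rule scores exactly 0, because its call is constant there.

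**Step 6: sensitivity to the derived frequencies.** For the Step 3 kit, with 2% instead of 4.05% in primary glioblastoma, kappa there falls to 0.46, while the pooled value is 0.64, 0.68, 0.66 and 0.61 at w = 10, 30, 50 and 80%. If IDH1 made up all IDH1/2 mutations (multiplier 0.90), kappa within types is 0.47-0.59, and the pooled value is 0.66, 0.67, 0.65 and 0.58 at the same shares. Only the last then fails.

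**The case against.** The strongest reply is that the Step 3 kit performs identically in every type, so pooling hides no difference in performance. What it exposes is a lenient cut-off and the absence of any required positive agreement. Much of this stands. The pooled kappa is simply kappa at the pooled frequency, and the plain defect is a rule that tolerates 62% positive agreement. That is why the remedy rests on agreement percentages. It does not rescue the rule, whose value still moves with a mix that the plan leaves open.

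Four stronger readings are tempting and are not supported.

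- **That the spread is between WHO classes.** It is between histological types. Table 1 puts primary and secondary glioblastoma together in Class IV. A rule reading only Class II-III against Class IV passes 0.6 only if secondary cases are below about 2.5% of Class IV (about 7% if all Class II-III samples are astrocytoma).
- **That a call from diagnosis alone generally passes.** It passes by a small margin in some mixes and fails clearly at 50% or more. With oligodendroglioma as the only mutation-rich type it peaks at 0.582. The kit is read from Ct and delta-Ct values (Section 4.1) and run blind (Section 3.4), so this rule is a benchmark and does not describe how the kit works.
- **That any mediocre kit passes.** The 70%/90% kit fails at a 30% share.
- **That kappa averaged over WHO classes would cure the problem.** Within Class IV, the diagnosis-only rule still reaches about 0.61 when 20-30% of cases are secondary (assumed shares). Kappa also penalises good kits at low frequency: 95%/95% agreement gives 0.90 at 61% but 0.58 at 4%.

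**Conclusion.** The point holds for the success rule in Section 5. With frequencies derived from the protocol's own background, one pooled kappa above 0.6 can declare a kit no different from sequencing although it misses 38% of mutations and has kappa of only 0.52-0.57 within each type. This holds for mutation-rich shares of 10-80%. Neither the subtype incidence count nor the unnamed comparison of results in Section 5 prevents it.

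The result assumes the 0.9 x 0.9 shares in every type, a kit with constant agreement across types, and a case mix that the plan does not state. The 4% is an upper bound and the 56-65% are near lower bounds. Varying them leaves the conclusion intact except at the 80% share. These calculations show what the rule permits. They are not evidence that this kit performs poorly.

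**What to change.** Revise Section 5 as follows.

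- Report positive and negative percent agreement with sequencing, each with a 95% confidence interval, overall in glioma and by recorded pathological diagnosis: grade II-III, primary glioblastoma, and secondary glioblastoma where the diagnosis separates them.
- Show non-glioma samples, which Section 3.2.2 admits, separately. If they entered the kappa they would inflate it further. With equal numbers of mutation-rich and primary glioblastoma samples, the Step 5 benchmark rises from 0.56 to 0.61 when 20% of all samples are non-glioma (assumed mutation-free).
- Rest the conclusion on these agreement figures together with kappa, with the minimum acceptable values written down before unblinding.
- Report kappa by diagnosis as supportive, noting that it is unstable at low frequency. Do not replace the pooled kappa with a weighted average of WHO-class kappas.

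The cost is a rewritten paragraph and some tables. Diagnosis is already recorded, so no new samples are needed. The protocol does not say whether that record distinguishes primary from secondary glioblastoma, so this should be checked with the sites. Subgroups with few positives will have wide intervals, and the conclusion may be less favourable than pooled kappa alone would give.
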